If the participant is receiving OBOT at Archway, he or she will have a 21-day medication taper and be assisted into transferring to community-based treatment..

Mishaps (lost or damaged smartphones).

Participants who lose or damage their smartphone during the study may be issued another one. (“Damage” is defined as anything that renders the smartphone permanently unusable for study purposes, including a cracked screen.) A second mishap will lead to discharge with a 21-day taper.

At the end of week 10, participants will return the smartphone to us. If this is their first issued smartphone and it is not damaged (as defined above), they may choose to keep it or return it for \$300. If this is their second issued smartphone and it is not damaged (as defined above), they may choose to keep it or return it for \$100.

Prior to the start of buprenorphine taper, OBOT participants will have the following choices: (a) to remain in the study through the taper phase, or (b) to transfer to another program.

Other procedural issues

Continuation of participants who have been hospitalized or incarcerated during the study: At any given time, it can be expected that several participants will be either hospitalized or incarcerated for short periods. If those participants return to the program immediately after their release, we will re-admit them to Archway after they are medically evaluated to resume. This can result in participants being in treatment for more than 16 weeks.

Because circumstances vary greatly across participants, we have chosen not to adopt a rigid cutoff for the maximum time a patient's participation can be delayed in this way. In the past, our informal cutoff has typically been about two weeks.

During a participant's incarceration, we will follow NIDA IRP procedures regarding research on prisoners: no data will be collected from the participant, and he or she will not be contacted by NIDA IRP staff or Archway staff. However, the participant will be permitted to inform Archway staff that he or she is incarcerated. After the participant is released, he or she will be permitted and encouraged to contact NIDA IRP staff or Archway staff and ask to be continued in the study. We will then decide whether to reactivate the participant, based on scientific and medical criteria.

Collection of data from incarcerated participants will not be an issue, because, like other personal property, the devices will be routinely confiscated by prison authorities upon entry and not returned until the prisoner is released. If the devices are returned to us and they somehow do contain data from time during incarceration, we will delete those data.

On some occasions, initiation of mobile data collection will begin later than scheduled. This typically occurs when the participant cannot meet with the experimenter at the appropriate time to receive the necessary introduction to the experimental condition. In all cases, all data collection will start as close as possible to the protocol schedule.

A 21-day taper will be offered to OBOT participants who choose to withdraw voluntarily from the study. Participants will also be discharged (with a 21-day taper for OBOT participants) if they meet one or more of the following termination criteria: (1) missing 4 (OBOT) or 3 (TE) study visits; (2) on 6 occasions, bringing in a dead smartphone following a missed clinic visit; (3) violating clinic rules; (4) failing to comply with smartphone data collection; or (5) losing or damaging two smartphones. In some cases, where disruptive behavior is a risk to staff or other participants, the OBOT taper may be less than 21 days. Any taper, whether administrative or voluntary, will include take-homes for Saturdays and Sundays.

H. Collection and storage of human specimens or data

Electronic data will be stored on the NIDA IRP's secure, password-protected system of electronic medical records (Clinical Data Warehouse; CDW). Paper records are stored in the Archway clinic under double lock in an area where individuals who are not part of the study staff do not have access (BRC building; room number 01B605). After the study is completed and data have been analyzed, the paper records will be stored at an NIH-approved commercial facility for the storage of sensitive data until approval for their disposal has been given.

Audio from the formative interviews will be sent without identifiers to a HIPAA-compliant professional transcription service. These services typically transcribe medical records. We will not permit the service to keep or share data. We will keep the transcripts indefinitely on secured servers. The audio will be accessible only to investigators and will be deleted when all interview data have been summarized—most likely within a year.

Stored biological specimens will be kept in a secure freezer in the Archway's NIDA freezer room until they are analyzed (BRC building; room 01B405). Specimens may be used for future analyses not described in the current protocol, but only after approval from the IRB. Any unplanned loss or destruction of the samples will be reported by the PI to the IRB.

Participants will be given the option of having their samples destroyed and/or having their data deleted, with the caveat that this might not be possible if the samples or data have already been shared (in an IRB-approved collaboration) with other researchers.

I. Statistical analysis

1. Outcome measures

Formative-interview phase

We are not using standardized questionnaires for the formative interviews, nor *a priori* cutoffs for outcome. Instead, this phase will be an iterative, collaborative process in which interviewees help us determine the extent and nature of changes to the content and interface of the JITAI app. We will replace any content (or interface elements) that multiple interviewees find confusing, unhelpful, or inappropriate. Any changes resulting from the formative interviews will, of course, be reflected in an amendment that the IRB will review.

As we note below, in the section on “gender/ethnic/race categories at risk,” focus-group data collected by another team of investigators in Washington, DC, show that low-SES African-American clinic attendees find mindfulness exercises helpful and empowering (Spears et al., 2017). This is an encouraging finding. A major purpose of our formative interviews will be to help ensure that our JITAI intervention is viewed similarly by the diverse groups of people for whom we intend it. If we notice any tendency for responses to differ by race, sex, or socioeconomic status, we may submit an amendment to expand the formative-interview phase.

Microrandomized trial

Proximal outcome measures (JITAI group only)

Decreases in problems in the 20 minutes from “pre” to “post” assessment
Ratings of usefulness at “post” assessment.

Distal outcome measures (JITAI group vs. EMA group)

FIT-60 mindfulness questionnaire (week 2 vs. week 11)
DTCQ for coping self-efficacy (week 2 vs. week 11)
COPE for coping-style flexibility (week 2 vs. week 11)
MCQ for delay discounting (week 2 vs. week 11)
Need for Closure scale (week 2 vs. week 11)
TSPQ-21 for Twelve-Step Involvement (week 2 vs. week 11)
opioid and other drug use (3x/week urine tests throughout study)

2. Analysis of study outcomes

Hypothesis 1, proximal: Main effect of messaging (delivery of either a CBT-based or ACT-based message will increase self-efficacy and decrease cravings and other negative states 20 minutes later, compared with the control message).

We will use multilevel random-intercept models (with data from the JITAI group only) to test the hypothesis of a proximal benefit of messages. The dependent variables, in separate models, will be participants' ratings of self-efficacy, craving, mood, and message helpfulness in EMA "post" assessments, controlling for the ratings in "pre" assessments. The main independent variable will be message type: active (CBT or ACT) versus none ("thank you" control condition). We will use an autoregressive error structure to account for within-person correlations. A significant beneficial effect on any of the outcome measures (self-efficacy, craving, mood, message helpfulness) will be taken as partial support for the hypothesis; significant beneficial effects on all the outcome measures will be taken as full support.

Hypothesis 2, proximal: Strategy-situation fit (the effects of the messages will be moderated by the circumstances in which they are provided).

The main analysis here (again, with data from the JITAI group only) will be a test of whether CBT messages are most effective in controllable situations and ACT messages are most effective in noncontrollable situations. We will categorize a situation as *noncontrollable* when a participant gives a response of less than 50/100 on either of these two "pre" items: (1) "I could easily be somewhere else right now if I wanted," (2) "I could easily get out of what I'm doing right now." Otherwise, we will categorize the situation as *controllable*. In the subset of instances in which an active message was given, multilevel models similar to those for hypothesis 1 will be run with the predictors Intervention Type (either CBT or ACT), controllability (y/n), and their interaction. A significant interaction (in the expected direction) on any of the outcome measures (self-efficacy, craving, mood, message helpfulness) will be taken as partial support for the hypothesis; significant beneficial effects on all the outcome measures will be taken as full support.

Other aspects of strategy-situation fit to be tested will include the setting (e.g., home, work, obligations, recreation), the nature of the problem (e.g., craving, boredom, anger), and cue exposure ("People, places, or things' are reminding me of drugs"). We will also examine alternative ways of operationalizing the controllability of a situation, because we know of no standardized way of doing so. In particular, we will examine the escapability of a situation in conjunction with its desirability, incorporating items such as "The place where I am is pleasant and comfortable (not too hot/cold, noisy, ugly, dangerous, etc.," "What I'm doing right now is

enjoyable for me,” and “What I’m doing right now is important to me.” We do not have *a priori* hypotheses for these analyses, and we will state that clearly when we report them.

Hypothesis 3, distal: Main effect of intervention (the group randomized to JITAI will have better outcomes—e.g. less drug use, higher self-efficacy, a greater increase in flexibility of coping styles—than the EMA-only control group when assessed at week 11).

These analyses, unlike the preceding ones, will use data from both the JITAI group and the EMA control group.

For group differences in mindfulness (FIT-60), coping self-efficacy (DTCQ), and coping-style flexibility (COPE), we will use analyses of covariance (ANCOVAs); in each ANCOVA, the dependent variable will be the score on the relevant measure at week 11, the categorical predictor will be group (JITAI vs. EMA) and the covariate will be the score at week 2.

The analyses on those questionnaire responses can be done only for participants who reach week 11. However, we will also test for a group difference in opioid use (thrice-weekly urinalyses) across the duration of the study. This analysis will use a generalized linear mixed model, so missing data (whether from early dropout or missed visits) will result in appropriately adjusted standard errors.

For a more stringent assessment of drug-use outcome, we will also compare the proportion of participants in each group who “succeed” in treatment (by completing week 11 and testing opioid-negative that week). Cessation of opioid use is not the main outcome measure for this study; we are more interested in psychological changes that might plausibly lead to good long-term outcomes. Nonetheless, we will assess and report this measure of treatment response.

Hypothesis 4, distal: Differential responses over time (CBT messages will be rated as helpful almost immediately; ACT messages may have to be lived with for several weeks, but may also stand up better to repetition).

In the JITAI participants, we will test this hypothesis with time-varying effect models (TVEMs) (Shiyko et al., 2012). These are extensions of multilevel models that can assess whether the relationship between a predictor and outcome becomes larger or smaller over time. If we see the predicted patterns of change on the “post” item “How useful was the message?,”

we will take that as full support for this hypothesis. If we see it only on other outcome measures (self-efficacy, craving, mood), we will take that as partial support.

Hypothesis 5, distal: Trait predictors of responsiveness (although we are not powering the study to assess treatment matching at the person level, we will examine whether trait variables such as personality and preferred coping styles are associated with differential responsiveness to CBT-based versus ACT-based messages).

This will be tested (with data from the JITAI group only) in multilevel models similar to those for hypothesis 1, with the predictors Intervention Type (either CBT or ACT), Trait, and their interaction. Specific predictions to be tested are: (1) high scorers on the baseline “Need for Closure” scale will benefit more from CBT messages than from ACT messages; (2) participants with steep discounting functions on the Monetary-Choice Questionnaire will be initially resistant to ACT.

The NEO personality inventory and our other trait measures offer many potential predictors, and we do not have *a priori* hypothesis for most of them. In reporting results from any of these analysis, we will specify that they were exploratory, and we will state clearly how many analyses we ran.

Hypothesis/analysis 6 (push versus pull: we will also assess, but have no directional predictions about, whether the intervention types that seem to benefit participants most when “pushed” by the app are the same ones that participants choose when subsequently given the opportunity to “pull” interventions).

For each participant in the JITAI group, we will use multilevel models with person-specific slopes to quantify the relative overall effectiveness of CBT vs. ACT messages during the “push” weeks, in terms of proximal changes craving, self-efficacy, and/or mood. We will then calculate the participant’s relative overall preference for CBT vs. ACT content during the “pull” week. These can be straightforwardly shown in a scatterplot with an accompanying bivariate correlation coefficient.

3. Criteria for statistical significance

The criterion for statistical significance will be set at $p \leq 0.05$, two-tailed. For hypothesized effects that do not reach statistical significance, we will calculate Bayes factors (Dienes, 2014), which help determine whether “nonsignificant” findings favor the null or the alternative hypothesis or whether they should be considered inconclusive.

J. Required sample size

For the formative-interview phase, we anticipate that 30 interviewees will be sufficient to give us feedback on our prototype materials and app interface. We may revisit this if we find that responses are highly variable across interviewees. We expect that most people who agree to be interviewed will provide usable information, so we are setting out enrollment ceiling at 35.

For the microrandomized trial, which is longer and more demanding, we expect a higher rate of dropout. We will enroll up to 150 participants to reach a target of 85 (50 JITAI, 35 EMA control) who complete the week-eleven outcome assessment. The calculations that led us to that total are as follows.

For hypothesis 1 (the proximal main effect of messaging in the microrandomized trial), we used a power-and-sample-size calculator <<https://pengliao.shinyapps.io/mrt-calculator/>> developed specifically for microrandomized studies (Liao et al., 2016). This calculation applies specifically to the JITAI group, not the EMA control group. As Liao et al. (2016) point out, there is very little precedent for determining what a proximal effect size should look like, but small studies with microrandomized designs can often detect seemingly small effects, on the order of $d = .15$. We decided that the most important consideration was to set our beta level high (.90, rather than the conventional .80), and we started by entering the following assumptions:

Days of study: 56 [eight weeks of “push” intervention].

Number of decision time points per day: 4.

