In the second part of the interview, we will show the the interviewee our plans (below) for a treatment app, using item lists, onscreen mockups, and/or functional demos. For all that material, we will ask interviewees to comment on its likely usefulness, its likely pitfalls or possible barriers to using it, and how we could improve it. We will also compile a wish list of app features and a list of things we should avoid.

Interviews will be audiotaped, and the tapes will be transcribed by a HIPAA-compliant service.

We have prior experience conducting this type of qualitative research with our participant population (Heinz et al., 2010).

3. Arm 1, Phase 2: Clinical trial with microrandomization

The following table shows the general timeline, which is explained in the sections that follow. *For analytical purposes, there are only two groups (JITAI vs. EMA control).* Procedurally, some participants will receive buprenorphine here at Archway (OBOT participants) and others will be treated elsewhere (TE participants). The recruitment of both OBOT and TE participants is not intended to bear directly on the science of the protocol; rather, it helps us enroll participants more quickly (our experience in the 020 protocol is that we enroll

an average of 4 OBOT participants and 4 TE participants every 30 days) and, as an additional advantage, may expand the population to which we can generalize our results (though we have not seen any appreciable demographic differences between OBOT and TE participants).

week	JITAI (OBOT)	EMA control (OBOT)	JITAI (TE: Treatment Elsewhere)	EMA control (TE: Treatment Elsewhere)
1	stabilize on bup; intro session (EMA + CBT/ACT); baseline questionnaires	stabilize on bup; intro session (EMA); baseline questionnaires	intro session (EMA + CBT/ACT); baseline questionnaires	intro session (EMA); baseline questionnaires
2				
3				
4				
5	JITAI – push 4x/day (first 16 nights will also include “Deep Dive” lessons/exercises on smartphone)			
6		EMA	JITAI – push 4x/day (first 16 nights will also include “Deep Dive” lessons/exercises on smartphone)	EMA
7				
8				
9				
10	JITAI – pull		JITAI - pull	
11	outcome assessment	outcome assessment	outcome assessment	outcome assessment
12				
13				
14	bup taper or transfer	bup taper or transfer		
15				
16				

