Participants in the formative-interview phase may reenroll for the randomized treatment phase. We want to give them access to the potential benefits of the intervention. When we analyze results, we will test whether the interviewed participants respond differently from newly enrolled participants, as might be expected from their having had input into the app design.

After signing informed consent, each participant will be randomly assigned to one of two groups: JITAI intervention or EMA only.

During the first two weeks of participation, each participant will have an in-person session for training appropriate to his or her study group. All participants will be shown how to use the smartphone to make entries. Participants randomized to the JITAI intervention will be introduced to some basic principles of CBT and ACT. We are forgoing extensive in-person training in the hope of demonstrating that our ambulatory intervention can be effective without that. Mindfulness and ACT, like CBT, can be learned through “unguided self-help” (that is, without in-person training) (Cavanagh et al., 2014). A mere 11 minutes of prerecorded audio instruction on mindfulness, delivered in a clinic, was superior to a relaxation control condition

in helping at-risk drinkers reduce their drinking over the next week (Kamboj et al., 2017). We will provide more support: during the initial in-person session, each participant will watch a video introduction to both CBT and ACT. The video will be approximately 20 minutes long, and will be recorded by a counselor who has experience delivering these kinds of interventions for addiction. We will use just one counselor to discuss both techniques to avoid any confounding by participant preference for one counselor over another.

Before and after the video, one of the investigators at our clinic will talk with the participant to address concerns and discuss any material that the participant found unclear. Investigators will also be available to answer participants' questions about CBT and ACT throughout their time in the study, either during clinic visits, or by phone or online.

The content of the video will be underscored and complemented by a series of lessons/exercises that participants will read at home on their smartphone, one per night, for the first 16 nights of the JITAI intervention. We describe the lessons/exercises (to be referred to as "Deep Dives") further down, after we describe the JITAI intervention.

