Baseline questionnaires to be administered during the first two weeks will include:

- The FIT-60 (Flexibility Index Test), a standard measure of traits associated with mindfulness (Batink et al., 2016), such as "I observe my feelings without losing myself in them" and "It is OK if I remember something unpleasant," and (reverse scored) "I believe that some of my thoughts are abnormal or bad and that I shouldn't think like that." We will readminister this at week 11 to test the hypothesis that mindfulness scores will increase more in participants randomized to the JITAI intervention group than in participants randomized to the EMA group.
- The DTCQ (Drug-Taking Confidence Questionnaire) (Sklar & Turner, 1999), an 8-item measure of coping self-efficacy in the context of resisting lapses to drug misuse. We will readminister this at week 11 to test the hypothesis that scores will increase more in participants randomized to the JITAI intervention group than in participants randomized to the EMA group.
- The COPE (Carver et al., 1989), a theory-based, empirically validated 60-item questionnaire assessing both general coping styles and coping behaviors in specific situations. We will use this to test whether preferred coping styles are

[figure not shown]
associated with differences in momentary responsiveness to CBT-based vs. ACT-based messages. We will also readminister it at week 11 to test the hypothesis that participants randomized to the JITAI group will begin to adopt a broader range of coping styles than those randomized to the EMA group.

- The Monetary-Choice Questionnaire (MCQ) (Kirby et al., 1999), a 27-item assessment of discounting of future rewards. We will administer this at baseline to test whether people with steep discounting functions are initially resistant to ACT. We will also readminister it at week 11 to test whether participants randomized to the JITAI group will begin to show less discounting.
- The Need for Closure scale (Kruglanski et al., 2013), a 47-item assessment of dislike for ambiguity and uncertainty. We will administer this at baseline to test whether high scorers benefit more from CBT messages than from ACT messages. We will also readminister it at week 11 to test whether participants randomized to the JITAI group (all of whom will be exposed to ACT) will begin to show less need for closure.

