We deliver buprenorphine treatment in a manner consistent with standard clinical care. It is necessary to deliver these forms of treatment within our research clinic because the required level of data collection would not be practical outside of treatment delivery or in a community clinic. Urine drug testing is a standard in clinical care; however, the frequency of collection (three times weekly) is greater than in most community treatment programs and is part of the research methodology in this protocol. All other measures are considered part of research.

The weekly counseling session will be delivered by a master's-level counselor at Archway. The focus will be on case management, meaning practical matters such as job searches, housing stability, medical/dental/insurance issues, and GEDs. Participants can also raise emotional issues as needed.

The timeline below is in chronological order (including duration of study, number of visits, and time commitment for participants).

Day 1: Consent and beginning of treatment

Participants will visit the clinic three days a week. Participants will be allowed to reschedule an appointment twice during the study if they miss an appointment or need to come in on an earlier day.

- Participants' buprenorphine will be stabilized during weeks 1 and 2 using flexible dosing under the supervision of the MAI.

Week 1-2: During the first two weeks, participants will undergo training appropriate to their randomized group; for the EMA control group, this will consist only of training on how to do EMA, not video material on CBT or ACT. Participants will also fill out baseline questionnaires, usually on a separate day.

End of Week 2

JITAI/EMA begins. Each participant will be issued a smartphone and reminded how to use it.

Week 11: Discontinuation of JITAI/EMA; outcome assessment.

- JITAI/EMA will end after week 10. Participants will be compensated for return of the smartphone.
- All participants will be readministered some of the baseline questionnaires (as specified above in the questionnaire descriptions) to assess changes in mindfulness, self-efficacy, need for closure, and coping styles.

Weeks 12-16: Optional buprenorphine taper for OBOT participants.

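### No rule puts the baseline questionnaires before the JITAI-only CBT/ACT video, so the week-2 covariate in the Hypothesis 3 ANCOVAs can be measured after part of the intervention in one arm

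*Combined protocol and SAP*

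**What the plan says.** **Randomization.** Section E.3: "After signing informed consent, each participant will be randomly assigned to one of two groups".

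**Video.** Section E.3 places it early: "during the initial in-person session, each participant will watch a video introduction to both CBT and ACT". The surrounding text and the précis confine it to the JITAI group, and section G confirms this: "for the EMA control group, this will consist only of training on how to do EMA, not video material on CBT or ACT".

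**Baseline questionnaires.** Section E.3: "Baseline questionnaires to be administered during the first two weeks will include" the FIT-60, DTCQ and COPE, among others. On their timing relative to training, section G says only: "Participants will also fill out baseline questionnaires, usually on a separate day".

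**Listing order.** The section E.3 table, for a JITAI participant treated elsewhere, reads "intro session (EMA + CBT/ACT); baseline questionnaires". Section G names training before questionnaires, under the remark "The timeline below is in chronological order". The précis (Methods) names the assessments before the video. Section S pays for the questionnaires in week 2. None of these is a sequence rule.

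**Analysis.** For FIT-60, DTCQ and COPE, section I.2 (Hypothesis 3) specifies an ANCOVA of the week-11 score on group, and "the covariate will be the score at week 2". The précis lists week-11 versus week-2 group differences in self-efficacy and coping flexibility as primary outcome 3.

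**The concern.** A baseline covariate protects a randomized comparison because treatment cannot have affected it. Here every baseline questionnaire is completed after randomization. The text also permits some or all JITAI participants to complete it after a video that control participants never see. If that video moves the scores, the ANCOVA treats part of the intervention's effect as a baseline difference between groups and adjusts it away.

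The scales are close to what the video teaches: the FIT-60 asks about observing and accepting feelings, the DTCQ about coping confidence, and the COPE about coping styles. Two of the three carry a primary outcome. A score not taken before the video cannot be recovered later, and the analysis section makes no provision for a baseline taken after it.

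**Working it through.** **1. The plan's own figures.** Section J powers Hypothesis 3 as a two-sample comparison with 50 JITAI and 35 control participants, two-tailed at .05. The standard error in SD units is √(1/50 + 1/35) = .2204.

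- At d = .70: noncentrality .70/.2204 = 3.18, df 83, power .881 (normal approximation .888). This agrees with the stated .90 to within two points.
- At d = .60: noncentrality 2.72, power .768 (normal .777), a little under the stated .80.

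These figures are context only. The point does not rest on them.

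**2. Inputs.** From the documents: n = 50 and 35, and two-tailed alpha of .05. I take d = .60 from section J as the true effect. Assumed, because the documents give no values:

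- b, the within-group slope of week-11 on week-2 score (equal SDs): .4 to .8, central value .6;
- s, the immediate upward shift from the video: 0 to .3 SD;
- f, the fraction of JITAI participants measured after the video: 1 (the most exposed case) or .5.

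**3. Formula.** If the JITAI mean of the covariate is raised by f × s, the ANCOVA group coefficient estimates d − f·b·s. Power follows from a noncentral t with df = 82 and noncentrality (d − f·b·s) / [√(1 − b²) × .2204]. With b = .6, √(1 − .36) = .8, so the denominator is .1763.

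**4. Results at d = .60, b = .6.**

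| s | Estimate, f = 1 | Power, f = 1 | Estimate, f = .5 | Power, f = .5 |
|---|---|---|---|---|
| 0 | .60 | .920 | .60 | .920 |
| .05 | .57 | .892 | .585 | .906 |
| .1 | .54 | .857 | .57 | .892 |
| .2 | .48 | .767 | .54 | .857 |
| .3 | .42 | .653 | .51 | .816 |

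Worked case, f = 1 and s = .2: .60 − .6 × .2 = .48, and .48/.1763 = 2.72.

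Simulation with 20,000 trials per cell gives, for f = 1, power .917, .854, .757 and .637 at s = 0, .1, .2 and .3. For f = .5 it gives .889, .847 and .809 at s = .1, .2 and .3. The formula is slightly optimistic.

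**5. Sensitivity to b (f = 1).** For b = .4, power is .835, .782, .720 and .651 at s = 0, .1, .2 and .3. For b = .8 it is .994, .973, .908 and .767.

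**6. ANCOVA or no covariate.** The unadjusted week-11 test has power .768 at d = .60 whatever s is. With f = 1, the shifted ANCOVA keeps more power until s = .60 × (1 − √(1 − b²))/b, which is .125, .200 and .300 for b = .4, .6 and .8.

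**The case against.** **The harm depends on unknowns.** No immediate video effect on these scales is given, and it is not known whether anyone would be measured after the video. The protocol's account gives reason to expect a small shift. The video is only an introduction, with the main teaching left to the 16 nightly lessons. Hypothesis 4 allows that ACT messages may need weeks before they are rated helpful. Section J starts message effects at d = .05, although that figure concerns momentary messages. On the other side, section E.3 cites 11 minutes of recorded instruction as reducing drinking, which is also not one of these scales. This objection stands as to size: at s = .05 to .1 with b = .6, power is still .89 to .86.

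**The order is not shown to be wrong.** A reader might infer from the table, or from section G's remark on chronology, that training is scheduled first. The documents do not support that. The chronology describes blocks of time, not the sentences within a block. The table cells for participants treated in-house open with buprenorphine stabilization, which runs through both weeks, so they are not sequences. The précis lists the items the other way round. The order is simply open.

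**False findings.** A reader might also infer an inflated false-positive rate in favour of control. With d = 0, b = .6 and f = 1, two-sided rejection would be .063, .103 and .172 at s = .1, .2 and .3. That requires a video shift that has vanished by week 11 despite eight more weeks of related content. If the shift merely persists (d = s), control-favouring rejection at b = .6 is only .004 to .014, below the nominal .025. Bias in favour of JITAI would need a video that lowers scores, and nothing in the documents suggests one.

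**Dropping the covariate has costs.** The ANCOVAs include only participants who reach week 11: a target of 85 from up to 150 enrolled. Only JITAI participants can be discharged for unfinished lessons. An unadjusted comparison loses adjustment for imbalance among completers as well as precision. This stands, and it limits that comparison to a sensitivity analysis.

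**Conclusion.** The point holds as a gap in the plan. The documents permit the covariate for a primary outcome to be collected after a component that one arm alone receives, and they contain no rule or analysis provision against it. They do not show that this will happen, or that the video moves these scores.

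For a video that helps, the error is conservative: the JITAI benefit is understated by about f × b × s. At b = .6 with everyone measured after the video, the loss is .03 to .18 SD for s = .05 to .3, and power at d = .60 falls from .92 to between .89 and .65. With half measured after it, power is .89 to .82 for s = .1 to .3. With no immediate effect there is no bias. All these sizes rest on assumed b, s and f.

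The change is worth making because a missed pre-video score cannot be recovered and prevention costs almost nothing.

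**What to change.** 1. State in section G (Week 1-2), and align the section E.3 table, that all baseline questionnaires are completed before the training session and video, ideally before the participant's allocation is disclosed. Record the dates of both.
2. Add to section I.2 (Hypothesis 3): if any participant completes the questionnaires after the video, report how many, and repeat the affected comparisons on unadjusted week-11 scores as a sensitivity analysis only. Say that it gives up precision and adjustment for baseline imbalance among week-11 completers. The ANCOVA remains the main analysis.

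The cost is one line on visit order, two recorded dates and a sentence or two of analysis text. No new data are collected. The downside is slightly less flexible scheduling in weeks 1-2.
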